#### **4.2.9.5 Change from baseline in pre-BD FEV1 and ACQ-6 overtime up to Week 52 (co-morbid asthma/AERD/NSAID-ERD subset)**

The same methods described in Section 4.2.7.2.2 for pre-BD FEV1 and Section 4.2.8.6 for ACQ-6 score will be applied through Week 76. Descriptive statistics including number of participants, mean, standard error, and LS means will be provided for each timepoint. In addition, the difference in LS means and the corresponding 95% CI will be provided for each timepoint.

#### **4.2.9.6 Proportion of participants with $\geq 1$ point reduction and $\geq 2$ points reduction in total NPS up to Week 52**

The same methods described in Section 4.2.8.7 will be applied through Week 52.

#### **4.2.9.7 Proportion of NCS responders up to Week 52**

A participant with  $\geq 1$  point reduction in NCS at Week 52 in the absence of SCS for NP, biologic for NP, or NP surgery at or prior to that timepoint will be defined as a responder, otherwise the participant will be defined as a non-responder. The number and proportion of NCS responders will be analysed as described in 4.2.7.2.1.

The same methods will be applied to each timepoint through Week 52.

### **4.2.10 Safety and Tolerability**

#### **4.2.10.1 Adverse Events**

All AE summaries will be presented by treatment group. AEs occurring during the screening/run-in period will be listed, but not summarised separately.

An overall summary table will be produced for the on-treatment and on-study periods showing the number and percentage of participants with at least one AE in each of the following categories: any AEs, SAEs, any AE with outcome death, and AEs leading to discontinuation of IP (DAEs). The total number of AEs in the different AE categories will also be presented. Key information of SAEs, AEs with outcome death, AEs leading to discontinuation of IP, and AESIs during the on-study period will be tabulated.

All AEs during the on-treatment and on-study periods will be summarised separately by SOC and PT assigned to the event using the MedDRA dictionary. An AE will be assigned into a period based on the onset date. For each PT, the number and percentage of participants reporting at least one occurrence of the event will be presented (ie, participants with multiple occurrences of the same PT will only be counted once).

Similar summaries by SOC and PT will be presented for the following during the on-treatment and on-study period:

- SAEs
- AE with outcome death
- AEs leading to discontinuation of IP (DAEs)
- Each AESI category separately
- The most common AEs (defined as those occurring in >3% of participants in either treatment group) – by PT only
- AEs by investigator's causality
- Each AESI category separately by investigator's causality

AEs are summarised by PT and maximum intensity during the on-treatment and on-study period. If a participant reports multiple occurrences of an AE within each PT, the maximum intensity will be taken as the highest recorded (the order being mild, moderate, and severe), respectively.

Exposure-adjusted AE (EAIR) summaries, and the difference in EAIR between treatment groups with 95% CIs calculated during the on-treatment and on-study period will be presented for each of the following summaries:

- overall AE categories: any AEs, SAEs, any AE with outcome death, and DAEs,
- All AEs by SOC and PT,
- SAEs by SOC and PT,

- DAEs by SOC and PT,
- Each AESI category by SOC and PT separately.

In the above summaries, the exposure-adjusted incidence rate (EAIR) will be calculated for each treatment as the number of participants in that treatment group reporting the AE divided by the total time at risk in that treatment group, where time at risk is the time to the first event for a participant who experienced the event during the analysis period and time during the analysis period for a participant who didn't experience the event. EAIR will be reported as events per 100 participant-years. The 95CI% for EAIR difference will be calculated based on Miettinen and Nurminen's score method.

The overall AE categories summaries for on-treatment and on-study period will be repeated for the following subgroups:

- Age group (<65,  $\geq$ 65 years)
- Gender (Male, Female)
- Race (White, non-White)
- BMI (<25,  $\geq$ 25 to  $<$ 30,  $\geq$ 30 kg/m^2)
- Region (Asia Pacific including China and Japan, Europe, North America)

The EAIR (95% CIs) by subgroups for all AEs and SAEs will be presented on the forest plots.

Overall AEs as well as AEs and SAEs by SOC and PT summaries will be produced for the AEs with onset date during the additional follow-up period for the Additional FU analysis set.

The number and percentage of participant reporting COVID-19 AEs (as defined based on the COVID-19 MedDRA terms) is summarised by SOC and PT for the on-treatment and on-study periods. In addition, if there are more than 10 participants reporting COVID-19 AEs, then the AE listing is repeated including only these participants, with details of all AEs reported by these participants.

The adjudicated adverse events will also be summarised at subject level and event level for placebo-controlled on-treatment and placebo-controlled on-study period. In addition, the adjudicated MACE events, serious cardiac events, death, and malignancy will be presented by SOC, PT and causality (as determined by the IAC). The adverse events sent for adjudication will be listed together with the outcome of adjudication.

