4.2 Scientific Rationale for Study Design

This is a global study designed to investigate the safety and efficacy of fixed dose tezepelumab (210 mg) administered SC starting at randomisation and then every 4 weeks (Q4W) for a total of 13 doses, on top of standardised INCS, in participants with severe bilateral NP who remain symptomatic despite standard of care therapy. To avoid bias the study will be randomised and double blinded. The population is composed of participants with ongoing chronic symptoms for at least 8 weeks prior to enrolment with moderate to severe participant reported nasal congestion, and a physician endoscopic diagnosis of bilateral NP (NPS of at least 5 out of a maximum of 8), despite documented treatment with SCS within the past 2 years and/or history of any NP surgical intervention. The disease severity at enrolment and history of failure with standard pharmacological treatment constitute an accepted indication for surgery or for a targeted biologic therapy such as tezepelumab, for participants who are not willing to or are contraindicated to have surgery.

CRSwNP is a heterogeneous disease ([Hull and Chandra 2017](#)). The eosinophilic (Type 2 high) endotype is most common in the United States, Europe, and Japan whilst non-eosinophilic endotype is more frequent in other Asian countries ([Lou H et al 2018](#), [Hull and Chandra 2017](#), [Fokkens et al 2020](#), [Shin SH et al 2014](#), [Chitsuthipakorn W et al 2018](#)). To ensure that endotypes are represented appropriately in all countries in this study capping will be used in China to ensure that approximately 80% of participants have an eosinophilic endotype

(defined by JESREC score of ≥ 11) ([Tokunaga T et al 2015](#)) to match the distribution predicted in the rest of the world.

The sample size (approximately 400 participants) is considered appropriate to demonstrate treatment effects with tezepelumab. The 52-week treatment duration is considered appropriate to capture maintenance effects in this chronic disease, assessment of endpoints of time to first SCS use and/or surgery (and the individual components), and proportion of participants with resolution/near complete resolution of nasal polyps as well as providing 1-year treatment safety data in the intended population. Approximately the first 200 randomised participants will have a 24-week follow-up period to evaluate durability of response and to provide off-treatment safety data.

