9.4.3 Safety

Adverse events will be coded using the Medical Dictionary for Regulatory Activities (MedDRA) version in force at each database lock. The definition of on treatment and post-treatment for adverse event analyses will be given in the SAP.

The number and percentage of participants with on treatment and post-treatment adverse events will be tabulated separately by preferred term and system organ class. An event that occurred one or more times during a period will contribute 1 observation to the numerator of the proportion. The denominator of the proportion will comprise all participants in the safety population. On treatment adverse events will also be summarised by intensity/severity and separately, by causality/relatedness (as determined by the investigator). Should a participant report the same preferred term/system organ class within multiple intensity/severity or causality/relatedness categories, the participant's worst occurrence (most severe/most related) will be tabulated. Adverse events, SAEs, AEs leading to death, and AEs leading to discontinuation of IP will be summarised for each treatment group as applicable.

An overall summary of on treatment AEs will be presented by treatment group adjusted for participant exposure to treatment.

AEs of Special Interest (AESIs), as defined in Section [8.3.6](#) will also be summarised descriptively by treatment group.

Laboratory data will be summarised by presenting shift tables using normal ranges (baseline to most extreme post-baseline value) and by presenting summary statistics of observed and change from baseline values (means, medians, quartiles, ranges). The incidence of clinically notable laboratory abnormalities will be summarised.

Vital signs data will be summarised by presenting summary statistics of observed and change from baseline values. The incidence of clinically notable vital signs abnormalities will be summarised. Abnormal ECGs as per Investigator's overall interpretation will be summarised.

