### 3.1.3 Study Periods

The following study periods are defined for analysis purposes:

- **Screening/run-in period:** starting on the date of the first study procedure and ending one day prior to randomisation (for randomised participants) or on the date of the last study procedure (for screening failures). If any participant is re-screened, the latest available screening will be used for this purpose.
- **Planned treatment period:** starting on the date of randomisation (efficacy) and ending on the date of the Week 52 visit or earlier study withdrawal date (for participants not followed up until Week 52). Unless noted otherwise, efficacy analyses will be based on planned treatment period.
- **On-treatment period:** starting on the date of first dose of IP and ending on the earlier (date of last dose of IP + 33 days, date of study withdrawal). Note: The 33 days is derived as dose frequency (28 days) plus 5 days as specified in the CSP Section 1.3.

- **Post-treatment period:** starting on the day after the end of the on-treatment period until the end of the study (Week 76 for the first ~200 participants and Week 64 for the remaining participants) or early withdrawal date.
- **On-study period** (planned treatment and follow-up): starting on the date of randomisation (efficacy) / date of first dose of IP (safety) and ending on the study completion or withdrawal date. For analyses performed at primary database lock, the on-study period is understood to include all data recorded up until the date of the data cut-off for the primary database lock (which includes all follow-up data available at the time of the data cut-off).
- **Additional FU period:** starting on the day after Week 64 visit until the end of the study (Week 76) or early withdrawal date. Only the first ~ 200 participants will continue follow-up beyond Week 64.

If a participant dies, the end dates of the study periods defined above will be capped at the date of death.

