### 3.6.2 General Adverse Events

Adverse events experienced by any participant at any time during the entire study will be coded using Medical Dictionary for Regulatory Activities (MedDRA V27.0). AEs will be categorised for analysis according to their onset date into the following study periods:

- AEs occurring during screening/run-in period: date of Visit 1 ≤ AE onset date < date of first dose of IP
- AEs occurring during on-treatment period: date of first dose of IP ≤ AE onset date ≤ earliest (date of last dose of IP + 33 days, date of death, date of study withdrawal)
- AEs occurring during post-treatment period: date of last dose of IP + 33 days < AE onset date ≤ study completion or withdrawal date
- AEs occurring during on-study period: date of first dose of IP ≤ AE onset date ≤ study completion or withdrawal date.
- AEs occurring during the additional FU period: date of Visit 19 ≤ AE onset date ≤ study completion or withdrawal date.

If the AE has a completely missing (and unresolvable) onset date, then the AE will be assumed to have occurred during the on-treatment period, unless the end date indicates unambiguously that the AE resolved before treatment started. If the AE has a partially missing (and unresolvable) onset date, then the AE will also be assumed to have occurred during the on-treatment period, unless either the end date indicates unambiguously that the AE resolved before treatment started, or the partial onset date is in the month/year prior to start of treatment.

The handling of partial/missing dates for AEs is detailed in [Appendix 8.3](#).

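### The SAP does not plan the separate post-treatment adverse-event tables that Protocol 9.4.3 specifies, leaving about 65% of planned post-treatment time without its own AE incidence table

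*SAP*

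**What the plan says.** Protocol 9.4.3 sets the requirement: "The number and percentage of participants with on treatment and post-treatment adverse events will be tabulated separately by preferred term and system organ class". It leaves the period boundaries to the SAP: "The definition of on treatment and post-treatment for adverse event analyses will be given in the SAP". It does not leave open whether the tables are produced.

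The SAP supplies the boundaries. Section 3.1.3 ends the on-treatment period 33 days after the last dose ("The 33 days is derived as dose frequency (28 days) plus 5 days as specified in the CSP Section 1.3"). Section 3.6.2 defines a matching category that starts where on-treatment ends: "AEs occurring during post-treatment period: date of last dose of IP + 33 days", running to study completion or withdrawal.

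Section 4.2.10.1 then plans AE tables for two periods: "All AEs during the on-treatment and on-study periods will be summarised separately by SOC and PT assigned to the event using the MedDRA dictionary". The on-study period is the treatment and follow-up periods together. The one off-treatment interval with its own summaries (overall AEs, and AEs and SAEs by SOC and PT) is defined by "AEs with onset date during the additional follow-up period for the Additional FU analysis set". That set is limited by SAP 2.1.3 to those of about the first 200 participants who completed the Week 64 visit.

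SAP Section 1 says that changes from the protocol will be described. Section 6 lists only added exploratory efficacy analyses.

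**The concern.** The category headed "AEs occurring during post-treatment period" is defined in SAP 3.6.2, but no AE table in 4.2.10.1 uses it. Concomitant medications, by contrast, do get a separate post-treatment table (SAP 4.2.4), so the gap is specific to adverse events.

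At stake is what the report can show about events arising after dosing stops. Protocol 4.2 gives one purpose of the 24-week follow-up of the first 200 or so participants as "to provide off-treatment safety data". With only on-treatment and on-study tables, post-treatment events appear pooled with a treatment period about three times as long. A difference between arms confined to the time after stopping would be diluted. The per-PT participant count that the protocol asks for would not be shown before Week 64 for anyone, or at all for the participants whose follow-up ends at Week 64.

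**Working it through.** The documents give no figure for this share, so there is none to reproduce. It follows from their dates.

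**Inputs**
- Last planned dose: Week 48 (SAP 1.2). Relative day = 7 × 48 + 1 = 337, matching the target day in SAP Table 1.
- End of on-treatment time: 337 + 33 = day 370 (SAP 3.1.3).
- Week 64 = day 449 and Week 76 = day 533 (SAP Table 1).
- About 400 participants: about 200 followed to Week 76 and about 200 to Week 64 (SAP 1.2).
- Assumption: everyone completes dosing and follow-up.

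**Post-treatment time**
- First 200: 533 − 370 = 163 days each.
- Other 200: 449 − 370 = 79 days each.
- Total: 200 × 163 + 200 × 79 = 48,400 days; 48,400 / 365.25 = 132.5 participant-years.

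**Time with its own AE summaries (after Week 64)**
- 200 × (533 − 449) = 16,800 days = 46.0 participant-years.

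**Time without**
- 48,400 − 16,800 = 31,600 days = 86.5 participant-years; 31,600 / 48,400 = 65.3%.
- First 200: 79 / 163 = 48.5% of their post-treatment time.
- Other 200: 100%.

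**Dilution**
- On-treatment: 400 × 370 = 148,000 days = 405.2 participant-years; 405.2 / 132.5 = 3.1.
- Post-treatment share of on-study time: 132.5 / (405.2 + 132.5) = 25%.

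**Sensitivity of the 65%**
- Counting weeks after the Week 52 visit: 1 − (200 × 12) / (200 × 24 + 200 × 12) = 66.7%.
- Counting the Visit 19 day in the additional period, as SAP 3.6.2 does: 64.9%.
- Long-follow-up group of 220 or 180 out of 400: 63.1% or 67.6%.
- If 95% or 80% of the first 200 enter the additional period and the rest stop at Week 64 (assumed): 66.4% or 70.2%.
- Early discontinuers who stay in the study add post-treatment time before Week 52 that also has no separate table.

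**What subtraction gives.** On-study is exactly on-treatment plus post-treatment. The overall AE table gives total event counts by category for both periods, so the difference is the post-treatment event count for any AE, SAEs, fatal AEs and AEs leading to discontinuation. The SOC and PT tables count a participant once per PT. For one PT, let *a* be participants with it on treatment, *b* participants with it on study, and *c* participants with it in both periods. Then *b* − *a* is the number whose first such event was post-treatment. The protocol asks for (*b* − *a*) + *c*. No planned table gives *c* over the full post-treatment period.

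**The case against.** A reader might infer that off-treatment safety cannot be read at all, or that no output covers the time between the end of treatment and Week 64. The documents do not support either. The on-study AE, SAE, death, discontinuation and AESI tables and their exposure-adjusted rates include that time. Key information on SAEs, deaths, discontinuations and AESIs is tabulated over the on-study period, and adjudicated events are summarised and listed. Subtraction recovers a good part of the rest. What is missing is the separate incidence table.

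A stronger defence concerns pharmacology. Protocol 8.3.12.2 equates 16 weeks with five half-lives. Counted from the last planned dose, that ends on day 337 + 112 = 449, which is Week 64. For participants who complete dosing, the time without its own table is therefore washout, and the largely drug-free time is what the SAP does tabulate. This is a reasonable ground for the Week 64 cut. However, the SAP does not state it, it does not hold for early discontinuers, and Protocol 9.4.3 makes no such split.

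Three further points stand. Protocol 4.2 attaches the off-treatment safety purpose only to the 24-week follow-up of the first 200 or so participants, alongside durability of response, so it should not be read as the purpose of all follow-up. Protocol 9.4 calls itself a summary and allows deviations to be reported in the clinical study report. And 9.4.3 does not require post-treatment exposure-adjusted rates or a period split for AESIs, so asking for those would go beyond the protocol.

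**Conclusion.** The two documents conflict. The protocol specifies post-treatment AE tables by PT and SOC; the SAP defines the period, plans no AE table for it, and does not declare the change. About 65% of planned post-treatment participant-time lacks a separate incidence table under full completion and an even split of follow-up lengths, and 63% to 70% under the variations tried.

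That percentage measures participant-time, not lost events or bias, and no hypothesis, estimand or error rate is affected. The loss is specific: the number and percentage of participants with a post-treatment AE by SOC and PT can only be partly inferred, with those who had the same PT on treatment hidden. The broader conclusion that off-treatment safety is unreadable does not follow.

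**What to change.** In SAP 4.2.10.1, add AE tables by SOC and PT, and the matching SAE table, for the post-treatment period as defined in 3.6.2, on the Safety Set by treatment group. Keep the after-Week-64 summaries as they are. If the sponsor prefers only the Week 64 cut, Section 6 should list the departure from Protocol 9.4.3 and give the reason.

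Post-treatment AESI tables and exposure-adjusted rates are optional extras. Complete follow-up is available only at the final database lock, because on-study data at the primary lock stop at the data cut-off (SAP 3.1.3); the new tables should therefore also be run at the final lock. SAP 2.1.4 closes the SAP to updates after the primary lock. If that date has passed, the tables can still be produced and the departure reported in the clinical study report.

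The cost is a few more tables, using existing layouts and a period category that the SAP already defines. No new data and no change to trial conduct are needed.

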#### 4.2.10.2 Laboratory Data

All continuous laboratory variables will be summarised by absolute value at each visit by treatment group, together with the corresponding changes from baseline. These summaries will be produced for the on-study period, as defined in Section 3.1.3. The summary statistics

presented will be the minimum, 1st quartile, median, 3rd quartile, maximum, mean and SD. Shift plots showing each individual participant's laboratory value at baseline and at maximum/minimum/last value post-baseline are produced for each continuous laboratory variable. If any laboratory variables show any unusual features (high or low values or a general shift in the data points) at other time points, then shift plots of these data may be produced. The diagonal line of no change is also displayed on the shift plots.

Central laboratory normal reference ranges will be used for the identification of individual clinically important abnormalities. A shift table will be produced for each laboratory variable to display low, normal, high, and missing values. The shift tables will present baseline and maximum/minimum/last post-baseline values for each variable.

The frequencies of clinically noteworthy values (using normal reference ranges) occurring during the study will also be given.

In order to identify potential Hy's Law cases, maximum post-baseline TBL is plotted separately against both maximum post-baseline ALT and AST, expressed as multiples of ULN. These plots are produced on a log scale, with reference lines included at 2xULN for TBL, and at 3xULN for both ALT and AST.

For all participants who meet the biochemical criteria for Hy's Law (potential Hy's Law cases), the relevant laboratory variables will be tabulated showing all visits for these participants. Participants with elevated ALT or AST in addition to elevated TBL at any time may be explored further graphically using individual participant profile plots, if indicated.

For urinalysis data, a shift table (separate for China and non-China participants) will be generated to present changes from baseline to maximum. All data for the on-study period will be used.

